8.7 Efficacy analyses

8.7.1 Alternate primary endpoint efficacy analysis

8.7.1.1 rPFS

Radiographic progression-free survival (rPFS) is defined as the time from the date of randomization to the date of radiographic disease progression as outlined in Prostate Cancer Working Group 3 (PCWG3) Guidelines (Scher et al 2016) or death from any cause. rPFS as determined by the independent central assessment will be used for this analysis. The primary analysis of rPFS will be based upon the PFS-FAS and will take place once 364 rPFS events have been reached. The allocated alpha level for the rPFS analysis is 0.004 1-sided.

Patients who are alive without radiographic progression at the analysis data cut-off or are lost to follow-up at the time of analysis will be censored for rPFS at the time of their last radiographic assessment or at the data cut-off date. rPFS data will be displayed using Kaplan Meier curves from which median rPFS times will be estimated for both treatment arms.

A stratified log-rank test model will be the primary statistical methodology used to analyze rPFS in the PFS-FAS dataset, stratified for the randomization stratification factors.

Supportive analyses of rPFS will be performed in terms of (i) a stratified Cox regression model on the PFS-FAS dataset with a single covariate for randomized treatment, and stratifying again for the randomization stratification factors; and (ii) the same as (i) but based upon the FAS dataset. The HR and CI from (i) will be used as an adjunct to the primary stratified log rank test p-value to provide the quantification of the treatment effect on rPFS.

8.7.1.2 OS

Overall survival (OS) is defined as the time from the date of randomization to the date of death from any cause and will be assessed in the FAS. A formal interim analysis of OS is planned to occur at the time of the rPFS analysis (with 364 rPFS events in PFS-FAS); it is anticipated that approximately 341 deaths will have accrued in the FAS at the time of the rPFS analysis in the PFS-FAS. The allocated alpha level for OS in this interim analysis is 0.001 1-sided. The final analysis of OS is event driven and will take place once 508 deaths have occurred in the FAS. As described in Section 8.3, the allocated alpha level for the final OS analysis will be between 0.020 and 0.025 1-sided, depending on the results of the earlier primary rPFS analysis and interim OS analysis.

Patients who are lost to follow-up or are alive at the time of the OS analysis (for both interim and final analyses) will be censored at the time they were last known to be alive or at the date of event cut-off for the OS analysis. OS data will be displayed using Kaplan Meier curves from which median OS will be estimated for both treatment arms.

OS will be analyzed using the same statistical methodology as described for the primary analysis of rPFS. Supportive analyses of OS will be performed at the interim and final in terms of Cox regression model on the FAS dataset with a single covariate for randomized treatment, stratifying for the randomization stratification factors. The HR and CI from these analyses be used as an adjunct to the primary stratified log rank test p-values to provide the quantification of the treatment effect on OS.

8.7.1.3 Statistical Interpretation of Alternate Primary Endpoints

The statistical design of the study is such that, to be declared positive, the study would be required to reach statistical significance on either the primary analysis of rPFS **or** OS at the respective allocated alpha level; it is **not required** to meet both rPFS and OS to be declared a statistically positive study.

Note, this applies to OS assessed at either the interim or the final analysis, i.e. for the study to be declared statistically positive requires rPFS to meet its allocated alpha level **or** OS to meet its

allocated alpha level at **either** (i) the formal OS interim analysis (conducted at the time of the rPFS analysis) **or** (ii) at the final OS analysis with 508 deaths.

Alpha allocation and recycling are used to ensure control of the overall Type I error rate as described in Section 8.3.

8.7.2 Secondary efficacy analyses

Key secondary endpoints

Key secondary endpoints will be subject to Type I error control. These endpoints are:

1. RECIST ORR and DCR
2. Time to SSE

The primary evaluation of these endpoints will be assessed in the PFS-FAS dataset. Time to SSE will be analyzed using a Cox regression model with a single covariate for randomized treatment, stratifying for the randomization stratification factors. ORR and DCR will be analyzed using logistic regression with a single covariate for randomized treatment and stratification for the randomization stratification factors. The odds ratio (active: control), its 95% confidence interval and associated 2-sided p-value will be presented. The DOR for binary response endpoint ORR will also be summarized and presented using Kaplan-Meier curves.

To control the overall Type I error rate, if either alternate primary endpoint is met, then the key secondary endpoints will be assessed using the Hochberg closed test procedure at the alpha level applicable to the successful alternate primary endpoint. This procedure is reasonable given the positive correlation between the two key secondary endpoints.

Supportive analyses of ORR, DCR and time to SSE will be performed in the FAS dataset using the same methods as described for the primary evaluation of these endpoints.

Additional Secondary Endpoints

Additional Secondary Endpoints will be assessed at the nominal 5% level, i.e. there will be no alpha control applied. These endpoints will be assessed in PFS-FAS with the exception of safety which will be assessed using the Safety analysis sets and are:

1. To evaluate the safety and tolerability of ^{177}Lu -PSMA-617
2. Aspects of HRQoL will be self-reported by patients (or via interview format) using the EQ-5D-5L and FACT-P questionnaires, and pain will be assessed by patients using the BPI-SF.
3. Health economics
4. PFS as defined as the date of randomization to the date of first evidence of radiographic progression, clinical progression, PSA progression, or death from any cause, whichever occurs first.
5. Biochemical response endpoints:
 - d. Proportion of subjects who are PSA responders, defined as a patient who has achieved a $\geq 50\%$ decrease from baseline that is confirmed by a second PSA measurement ≥ 4 weeks.

- e. Alkaline phosphatase [ALP] and lactate dehydrogenase [LDH] levels will also be collected.

Event-free survival endpoints (e.g., PFS, time to pain worsening) will be analyzed using a Cox regression model in the same manner as described for time to SSE except using a 2-sided p-value. DCR will be analyzed in the same manner as ORR and HRQoL will be analyzed in the same manner as pain score over time. Time to pain improvement response after initial pain worsening will be analyzed using mixture distribution methodology akin to that described by Ellis et al 2008.

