8.2.2 Key Secondary Efficacy Analyses

Refer to Section 8.2 for analysis sets and presentation of summary statistics. To control the overall Type I error rate, if either alternate primary endpoint is met (see Section 4), then the key secondary endpoints will be assessed using the Hochberg closed test procedure at the alpha level applicable to the successful alternate primary endpoint. This procedure is reasonable given the positive correlation between the key secondary endpoints.

The alpha level applicable to the analysis of the key secondary endpoints will depend on the statistically significant results of the final rPFS or the statistically significant results of OS at either the interim or final analysis as follows:

Analysis of Key Secondary Endpoints at Interim and Final OS Analysis

Scenario	Final rPFS/Interim OS Analysis			Final OS Analysis	
	Final rPFS 1-sided p-value	Interim OS 1-sided p-value	2-sided alpha (CI) for Key Secondary Endpoints	Final OS 1-sided p-value	2-sided alpha (CI) for Key Secondary Endpoints
A	p<0.004	p<0.001	0.01 (99%)	Not re-tested ¹	Not re-tested ²
B	p<0.004	NS	Not tested ³	p<0.024	0.048 (95.2%)
				NS	Not tested ⁴
C	NS	p<0.001	0.002 (99.8%)	Not re-tested ¹	Not re-tested ²
D	NS	NS	Not tested ³	p<0.02	0.040 (96%)

NS: Not statistically significant at pre-specified alpha level.

CI: Confidence interval

- Final OS will not be re-tested if the interim OS is met. The final OS results will be presented descriptively including 95% CI and the nominal p-value.
- The key secondary endpoints will not be re-tested if the final OS is met however, the results will be presented descriptively including 95% CI and the nominal p-value.
- The key secondary endpoints will not be tested if interim OS is not met however, the results will be presented descriptively including 95% CI and the nominal p-value.
- If the key secondary endpoints are tested when final OS is not met using the successful rPFS 1-sided (2-sided) alpha level of 0.004 (0.008), there will be, at most, a type I error inflation of 0.004 because the rPFS alpha level has already been allocated to the final OS test. Therefore, if final OS is not met, the key secondary endpoints will only be presented descriptively including 95% CI and the nominal p-value.

Analysis of Key Secondary Endpoints at Final rPFS/Final OS Analysis

Final rPFS/Final OS Analysis			
Scenario	Final rPFS 1-sided p-value	Final OS 1-sided p-value	2-sided alpha (CI) for Key Secondary Endpoints

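### Protocol 8.7.2 and the opening of SAP 8.2.2 allow the key secondaries to be tested at 1-sided 0.004 after rPFS success alone, although that 0.004 has already passed to final OS; the SAP tables say the opposite

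*Protocol*

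**What the plan says.** **Rule for opening the key secondaries.** Protocol 8.7.2 places ORR, DCR and time to SSE inside the error claim: "Key secondary endpoints will be subject to Type I error control". It then states that "if either alternate primary endpoint is met, then the key secondary endpoints will be assessed using the Hochberg closed test procedure". As to the level, the same sentence has this testing done "at the alpha level applicable to the successful alternate primary endpoint". The SAP 8.2.2 lead-in has the same rule: "if either alternate primary endpoint is met (see Section 4), then the key secondary endpoints will be assessed using the Hochberg closed test procedure".

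**Alpha for the primaries.** Protocol 8.7.1: "The allocated alpha level for the rPFS analysis is 0.004 1-sided" and "The allocated alpha level for OS in this interim analysis is 0.001 1-sided". Protocol 8.3 and SAP 3.4 set final OS at 0.020 if neither earlier test succeeds, and at 0.024 if rPFS succeeds and interim OS does not. SAP 4 adds a path with no interim OS analysis, where final OS is tested at 0.025 after rPFS success and at 0.021 otherwise. Protocol 8.3 claims an overall 1-sided Type I error of at most 0.025.

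**SAP 8.2.2 tables.** When rPFS is met and OS is not, both tables (with and without an interim OS analysis) mark the key secondaries as not tested, and the footnotes make them descriptive. The reason given is that testing them would bring, at most, "a type I error inflation of 0.004 because the rPFS alpha level has already been allocated to the final OS test".

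**Declaration of the change.** SAP 2.1 lists several departures from Protocol 8.7.2 (analysis set for ORR and DCR, log-rank test for SSE) but not this one. The SAP's revision history for version 3.0 says only that the testing rules for the key secondaries were clarified.

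**The concern.** In a Bonferroni-type scheme with recycling, alpha released by a rejected hypothesis can go to one place, or be split, but cannot be used in full twice. The plan sends all of the rPFS alpha to final OS. Protocol 8.7.2 and the SAP lead-in then use the same 0.004 again for the key secondaries.

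The outcome that matters is rPFS positive and OS negative. Under Protocol 8.7.2, ORR, DCR and SSE could then be claimed as error-controlled findings at 2-sided 0.008. Under the SAP tables, nothing could be claimed. No sentence says that the tables override the SAP's own lead-in. Protocol 8.2 also undertakes to amend the protocol if methods for the key secondary hypotheses change. SAP 3.0 is dated 18 January 2021, and the protocol was amended three times after that (V5.0 to V7.0) with the sentence left in place.

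**Working it through.** **1. Reproduce the plan's own figure.** Allocated alphas for the primaries (Protocol 8.3 and 8.7.1): rPFS 0.004, interim OS 0.001, final OS 0.020.

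0.004 + 0.001 + 0.020 = 0.025, which matches the stated bound. The primaries use all of it.

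**2. Error bound when rPFS alone opens the key secondaries.** Take rPFS truly improved and rejected with certainty, with OS and all key secondaries null. A false rejection can come from:

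- interim OS: 0.001
- final OS, after receiving the rPFS alpha: 0.020 + 0.004 = 0.024
- the Hochberg family at the rPFS alpha: 0.004

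Sum: 0.001 + 0.024 + 0.004 = **0.029**. With no interim OS analysis (SAP 4): 0.025 + 0.004 = **0.029**. The excess over 0.025 is 0.004, the figure in the SAP footnote.

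**3. Bound under the SAP tables.** With rPFS met, the key secondaries are tested only after OS is met. If OS is null, a false key-secondary claim needs a false OS claim first. The bound is 0.001 + 0.024 = 0.025, or 0.025 on the no-interim path.

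**4. Bound if rPFS is also null.** Any rejection must begin with a false rejection of rPFS or OS, so the bound stays at 0.004 + 0.001 + 0.020 = 0.025.

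**5. How close the error comes to 0.029.** Interim and final OS statistics are correlated: information fraction 341/508 = 0.671, correlation √0.671 = 0.819. The bivariate normal probability of rejecting OS at 0.001 or 0.024 is 0.0241, slightly below 0.025. I then simulated OS null, key secondaries null and rPFS success certain, with Hochberg on three endpoints at 1-sided 0.004 (6 million replicates, simulation standard error about 0.00007). The documents give no correlations, so those below are assumptions.

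| Correlation among key secondaries | Correlation of each with OS | Error, with interim OS | Error, no interim OS |
|---|---|---|---|
| 0 | 0 | 0.0278 | 0.0287 |
| 0.5 | 0 | 0.0278 | 0.0287 |
| 0.5 | 0.3 | 0.0273 | 0.0282 |
| 0.5 | 0.5 | 0.0266 | 0.0275 |
| 0.9 | 0.5 | 0.0261 | 0.0270 |
| 0.64 | 0.8 | 0.0248 | 0.0257 |

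The error exceeds 0.025 unless the key secondaries track OS very closely.

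**The case against.** The strongest reply is that the SAP has already dealt with this. Its tables cover rPFS met with OS not met on both paths, its footnotes name the same 0.004 and the same cause, and the key secondaries become descriptive. Protocol 8 makes the SAP the detailed account of the methods. The SAP lead-in can also be read as a summary that the table below it makes specific, since the following paragraph says that the alpha depends on the results and then presents the table. SAP 2.1 at least sends the reader to 8.2.2. Much of this stands: an analyst who follows the tables keeps 0.025.

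It does not remove the conflict. Protocol 8.7.2 has no table to qualify it, and its literal rule gives the wrong result in the rPFS-positive, OS-negative case. The sentence introducing the SAP table still offers rPFS or OS significance as alternatives.

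A second reply is that 0.029 is a ceiling. That is right. It needs rPFS truly effective and the key secondaries null along with OS. That combination is narrow, because ORR, DCR and part of rPFS all rest on soft-tissue imaging. Strong control must nevertheless cover it.

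Two stronger readings are tempting, and the documents support neither. A reader might infer that the trial's analysis will run at 0.029. It will not if the tables are followed. A reader might also infer that the alpha split between rPFS and OS is faulty. It is not: the primaries alone sum to 0.025.

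**Conclusion.** The point holds as a contradiction between a stated rule and the SAP tables, with a definite consequence if the rule is followed. Protocol 8.7.2 and the SAP 8.2.2 lead-in allow the rPFS alpha to be used twice. The familywise bound is then 0.029 against the stated 0.025, an excess of at most 0.004. It applies only when rPFS is effective and both OS and the key secondaries are null.

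For assumed correlations with OS of 0 to 0.5, the simulated error with the interim is about 0.027 to 0.028, falling to 0.026 if the key secondaries are also highly correlated with one another. At a correlation with OS of 0.8 it is 0.0248. The SAP tables are correct and keep 0.025. The sentences that contradict them need changing, and the change from the protocol should be declared.

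**What to change.** In Protocol 8.7.2 and the SAP 8.2.2 lead-in, make testing of the key secondaries conditional on OS being met at the interim or final analysis. Replace the phrase "at the alpha level applicable to the successful alternate primary endpoint" in the protocol, and its counterpart in the SAP, with a reference to the SAP 8.2.2 tables. Align the SAP sentence that introduces the tables, so that rPFS significance alone no longer appears as a route to testing. Add the change to SAP 2.1.

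The wording is exact, because every cell of the two tables in which the key secondaries are tested already requires OS success. The cost is a few sentences and one list entry. It gives up an error-controlled secondary claim on rPFS alone, which the SAP tables have already given up. If the final analysis has been done according to the tables, no result changes; the correction then fixes which secondary claims the documents treat as error-controlled.

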8.8 Safety analyses

All safety evaluations will be based on the Safety Analysis Set.

8.8.1 Extent of exposure

The duration of exposure and dose intensity will be calculated. The relationship between dose intensity, duration of exposure, and frequency and severity of adverse events will be explored by data tabulation.

8.8.2 Analysis of adverse events

The frequency of treatment emergent adverse events (TEAEs) and SAEs will be tabulated by Medical Dictionary for Regulatory Activities (MedDRA) preferred term and system organ class. The maximum NCI CTCAE grade and frequency of AEs will be summarized.

A ⁶⁸Ga-PSMA-11 TEAE is defined as an AE that was not present prior to dosing with ⁶⁸Ga-PSMA-11 but appeared following dosing or was present at time of initial dosing but worsened during or after dosing. The treatment-emergent period will be defined as the period from the date of ⁶⁸Ga-PSMA-11 dosing up to 6 days after the date of ⁶⁸Ga-PSMA-11 dosing as long as prior to the first dose of ¹⁷⁷Lu-PSMA-617 for the investigational arm and Cycle 1 Day 1 for the best supportive/best standard of care-only arm. Adverse events reported as “possibly”, “probably”, or “definitely” related to ⁶⁸Ga-PSMA-11 that occur beyond the 6-day reporting window but occur before the initiation of randomized treatment are also ⁶⁸Ga-PSMA-11 TEAEs. Unrelated ⁶⁸Ga-PSMA-11 adverse events that occur beyond 6 days will not be TEAEs.

A randomized treatment TEAE is defined as an AE that was not present prior to initiation of randomized treatment, defined as first dose of ¹⁷⁷Lu-PSMA-617 for the investigational arm and Cycle 1 Day 1 for the BS/BSC arm, but appeared following treatment, or was present at treatment initiation but worsened during treatment. An AE that was present at treatment initiation but resolved and then reappeared while the patient was on treatment is a TEAE (regardless of the intensity of the AE when the treatment was initiated). The treatment-emergent period will be defined as the period from the initiation of randomized treatment up to 30 days after the date of the last dose or intervention of randomized treatment or the day prior to the initiation of subsequent anticancer treatment, whichever occurs first.

Adverse events leading to permanent discontinuation of study drug and/or leading to death will be listed and tabulated.

8.8.3 Analysis of laboratory assessments

Laboratory values and change from baseline will be summarized by visit and treatment using descriptive statistics. Shift tables of the worst on-study laboratory toxicity based on CTCAE v5.0 grading relative to baseline will be presented by treatment group. Subject listings of laboratory toxicities \geq Grade 3 will be provided.

8.8.4 Analysis of vital sign data

Vital sign data (observed and change from baseline) will be summarized using descriptive statistics by time point and treatment. Abnormal findings from physical examinations will be assessed for clinical significance which will be included in the AE listings and summaries.

8.9 IDMC and Interim Data Evaluation

8.9.1 IDMC

An IDMC will be convened to review accumulating safety and safeguard patient interest in the study. Safety data monitoring will be conducted quarterly by the IDMC. These safety reviews will commence following the completion of the first three months of study accrual.

In addition, a summary of efficacy data will also be provided to the IDMC at the time of routine safety data reviews; these efficacy data will be provided for information only, no statistical analyses will be conducted. The only analyses of efficacy data are those formally planned for rPFS in the PFS-FAS at 364 events, interim OS (in the FAS) at the time of the rPFS analysis and final OS (in the FAS) with 508 deaths.

The IDMC will review these formal efficacy analyses. The IDMC may recommend early curtailment of trial on the basis of meeting one of the preplanned formal efficacy analyses or due to the emergence of an unforeseen safety concern placing patient safety at risk.

An IDMC Charter will be approved and finalized by the IDMC members prior to the initiation of any formal efficacy analysis.

The IDMC can recommend a course of action, but the sponsor will make the final decision regarding whether or not to continue or stop the trial, based on any analysis for reasons related to safety or efficacy.

8.9.2 Formal Interim Analysis of OS

As described above in Section 8.3, one formal interim analysis is planned for OS in the FAS to take place at the time of the primary rPFS analysis in the PFS-FAS. The allocated alpha level for the interim OS analysis is 0.001 1-sided. Regardless of whether a positive result is attained at this time, for either rPFS or interim OS, patient follow-up will continue until 508 OS events have accrued in the FAS at which time a final OS analysis will be performed.

9. ACCESS TO SOURCE DATA/DOCUMENTS

During the course of the study, a representative of Endocyte or its designee will be contacting and/or visiting the study sites to monitor the progress of the study. Contacts with the investigator and on-site visits for the purpose of data audits, including the comparison of source documents

with case report forms (CRFs) and study agent accountability logs, will occur. The principal investigator or his/her representative will need to be available to the representative of Endocyte or its designee during these visits.

By signing the protocol, the investigator acknowledges that, within legal and regulatory restrictions and institutional and ethical considerations, Endocyte, its designee, or responsible government agencies (as required by law) may review or copy source documents in order to verify case report form (CRF) data.

10. ETHICS

10.1 Institutional Review Board/Independent Ethics Committee/ Research Ethics Board (IRB/IEC/REB)

The investigator will obtain approval from the IRB/IEC/REB of the proposed clinical protocol and ICF for study recruitment and the approval will be provided to Endocyte or its designee prior to beginning the clinical trial. The only circumstance in which a deviation from the IRB/IEC/REB-approved clinical protocol/ICF may be initiated in the absence of prospective IRB/IEC approval is to eliminate an apparent immediate hazard to the research participants. In such circumstances, the investigator will promptly notify the IRB/IEC/REB of the deviation.

The investigator will promptly notify Endocyte of any regulatory inspection relating to this study, including either the institution or the IRB/IEC/REB, and will promptly provide Endocyte with a copy of any inspection report.

